Overall, because our outreach program already includes all outreach intervention components recommended by the Task Force on Community Preventive Services, and because financial incentives show promise for changing health behaviors that are far more complex than completing FIT screening, we need to determine whether financial incentives boost CRC screening over and above our organized outreach program. Our proposed prevention program will determine whether offering financial incentives, in the form of either a \$5 or \$10 gift card in exchange for screening completion, are an effective adjunct to our organized outreach approach.

BACKGROUND SUMMARY. CRC is an important public health problem, particularly for the uninsured, who have the lowest screening rates and worst CRC outcomes. Our prior, CPRIT sponsored Evidence based Prevention program focused on the uninsured was successful in boosting

screening participation by 29%. Organized outreach was twice as effective when patients were offered FIT vs. colonoscopy screening (33% vs 14%). Our program was highly evidence based and successful, but several challenges remain. We must expand our organized outreach to all individuals eligible for screening. Program sustainability must be ensured by transferring primary responsibility for screening promotion delivery to JPS. We must determine if participation rates remain high when screening is offered annually because effective, evidence based FIT screening requires annual test completion. Finally, innovation is required. Offering modest financial incentives to complete screening, beyond offering free tests, may be a particularly effective adjunct to our current outreach approach. The specific aims and outreach approach outlined below have been carefully crafted to leverage the screening needs of the uninsured, our prior experience with a successful outreach program, and innovative ideas for screening to improve CRC screening to deliver screening and advance evidence based screening practice.

Concise Summary of Project:

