Centralized processes to promote guideline-based follow up. Follow up for patients with a normal test in Year 1 will consist of repeat screening invitations in Year 2 and Year 3. This is consistent with guideline recommended annual FIT for CRC screening^{13, 14}. Follow up for patients with an abnormal FIT will consist of navigation to complete a colonoscopy. Up to 10% of individuals with an abnormal FIT have a colon cancer, and up to 50% may have a potentially precancerous polyp^{44, 45}. Thus, colonoscopy follow up is imperative. Patients with abnormal FIT will be called by the screening team within 1 week to report the result and facilitate direct scheduling of colonoscopy or a pre-colonoscopy visit. During their pre-colonoscopy visit patients will receive a Gatorade Bowel Prep kit with instructions on how to prepare for their colonoscopy. If colonoscopy scheduling is delayed, there is a possibility that the Dulcolax tablets in prep kits may expire. Expiration dates will be monitored by the study team. In the event tablets will reach expiration before a scheduled colonoscopy, the patient will be mailed a letter with replacement tablets. The goal will be to schedule colonoscopies within 12 weeks of the abnormal FIT. In our prior outreach program, all patients willing to have their colonoscopies done within 12 weeks were accommodated, most within a much shorter period of time. Patients who do not keep their scheduled pre-colonoscopy or post-colonoscopy appointment will be contacted by phone to reschedule their missed visit. Patients who the study team are unable to contact by phone will be mailed a "No-Show" letter asking them to call the JPS clinic to reschedule their appointment. Similarly, patients who do not keep their scheduled colonoscopy will be contacted by phone to reschedule their colonoscopy. Those patients that the team is unable to contact by phone will be mailed a "No-Show" letter asking them to contact the JPS clinic to reschedule their colonoscopy. After multiple attempts to reach No-Show patients by phone and certified letter, a final letter will be mailed to them. The letter informs patients that this is the final attempt to remind them that they had an abnormal FIT and to contact the JPS staff to schedule an appointment for further evaluation, possibly with colonoscopy. All three letters will be on JPS letterhead signed by [name] and include a contact phone number for the study team.

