The incentive will consist of either a \$5 or \$10 gift card to a local retailer that will be sent to the patient upon return of an FIT kit. Incentives will be mailed by the JPS outreach team, in exchange for successful FIT completion, after the FIT has been returned. \$5 and \$10 incentives were chosen for several reasons. First, these levels of incentives, if shown effective, could be potentially sustained by the JPS system beyond the timeframe of the grant. Higher incentives, while potentially more powerful in inducing participation, would be unsustainable and therefore do not merit study at this time. Comparing \$5 and \$10 incentives is important because if offering incentives is effective in boosting screening, it is important to know the minimum incentive required for meaningful changes in participation. Incentives are to be offered to all patients who are assigned to the incentive strategy. We considered, but rejected, restricting incentives to only patients who initially do not respond to screening invitations. This was because restricting incentives to non-responders would logistically complicate outreach activities. It is important to note that patients meeting study inclusion criteria must have a minimum of 1 visit to a JPS Primary Care clinic within the last year. Considering these patients have an established baseline relationship with the JPS primary care system, the addition of a modest financial incentive should not create undue influence in patients that otherwise would still have exposure to information on the benefit of screening. Since participation in this standard of care screening poses minimal to no risk, the chances that incentives may motivate research participants to take unnecessary risks are low.

Screening Completion Follow Up. Follow up for determining screening completion for all included patients will be through the end of Year 3 regardless of whether or not patients respond to screening invitations. As is explained below, screening rates will be measured for all patients included for outreach invitations. For patients who die on follow up or who do not have additional health system encounters, follow up will be censored at time of death or last health encounter, respectively.

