Uninsured patients not up-to-date with CRC screening meeting the following criteria will be included:

- Age 50-64. This age group is at highest risk for screening non completion. Patients younger than age 50 will be excluded because screening is not routinely recommended for patients under 50. Patients older than 64 will be excluded because most of these patients would have screening access through Medicare insurance.
- Uninsured, but participants in JPS's medical assistance program for the uninsured. Uninsured patients have the lowest rates of screening participation, and therefore are most likely to benefit from screening outreach. Selecting patients who are uninsured, but enrolled in JPS's medical assistance program for the uninsured will ensure that any patient found to have a cancer or unresectable polyp will have access to surgical and/or medical oncology services. This is critical, because CPRIT funds do not allow for cancer care; offering screening without a system to care for patients with cancer would be unethical.
- One or more visits to a JPS primary care clinic within a year. This criterion establishes that patients have a baseline relationship with the JPS primary care system.
- Not up-to-date with colorectal cancer screening. We will apply National Committee on Quality Assurance Healthcare Effectiveness Data and Information Set (HEDIS) criteria to determine if patients are up-to-date with screening, defined by having had a colonoscopy within 10 years, a fecal occult blood test within one year, or a sigmoidoscopy within 5

Table 3: HEDIS codes used to measure CRC Screening			
Description	СРТ	HCPCS	ICD-9-CM Procedure
FOBT/FIT	82270, 82274	G0328, G0394	
Sigmoidoscopy	45330-45335,45337- 45342,45345	G0104	45.24
Colonoscopy	44388-44394,44397, 45355, 45378-45387, 45391, 45392	G0105, G0121	45.22, 45.23, 45.25, 45.42, 45.43

years⁴³. HEDIS criteria allow for using administrative claims data, including Current Procedural Terminology (CPT), International Classification of Diseases-9 (ICD9), and Health Care Common Procedure Coding System (HCPCS) codes to determine whether patients have had CRC screening tests. Logical Observation Identifiers Names and Codes (LOINC) will not be used because these are not routinely used within the JPS system.

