 HEDIS criteria were selected because these are standardized criteria that the National Committee on Quality Assurance uses to compare rates of CRC screening across different insurance carriers. The criteria are clear, and widely available, and using these criteria will improve generalizability of our program procedures. In prior published analyses, we previously demonstrated ability to determine screening rates and identify patients not up to data using a similar approach, and validated the approach for this purpose^{19, 42}. Table 3 shows codes that will be used to assess whether patients are screening up-to-date.

Criteria for Exclusion of Subjects:

Patients with a history of CRC or colon resection, no address and/or phone number on file, or who are incarcerated will be excluded. Patients with history of CRC/colon resection will be excluded because they require specialized screening, usually with colonoscopy. Addresses and phone numbers are required to deliver outreach. Incarcerated patients will be excluded because they cannot keep FIT kits in their cells.

Once included, patients will remain in the program unless they no longer meet age criteria. Patients in both the standard (non-incentive) and incentive invitation groups who do not respond to initial invitation will be followed for screening outcomes, but will not receive repeat

Version 8, June 29, 2015

invitations. Through the program period, we expect that some patients will no longer participate in the JPS connection program, or not see a primary care provider within a year. We considered excluding these patients in subsequent years, but decided against this. Many of these patients remain uninsured, and if they were to develop late stage CRC, would present to JPS for treatment. We anticipate that most of these patients would then again access the JPS medical assistance program for the uninsured as well as primary care clinics, because JPS is the main safety-net health system for uninsured patients in Tarrant County and Fort Worth, TX. Continuing screening outreach will potentially allow for boosting detection of such patients when their CRCs are early, rather than late stage.

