we will even have 90% power to detect a smaller screening rate increase of \geq 5% (Power was computed with nQuery Advisor Software v.7.0).

Evaluation Aim B) Compare rates of initial and repeat screening completion among 1) Patients offered a modest financial incentive to complete screening, in addition to outreach invitations (n=2,000), vs. 2) Patients offered outreach invitations alone (n=~18,000). The rate of initial screening completion will be defined by:

Initial	# patients completing a FIT
Screening	Year 1
Completion Rate =	# of patients sent FIT invitation Year 1

We will compare the initial screening completion rate for patients offered the financial incentive, in addition to screening outreach, to the initial rate for patients offered screening outreach alone using a Chi-square test of proportions, with a 2-sided p value <0.05

considered statistically significant. The rate of repeat screening for Years 2 and 3 will be defined by:

Year 2	# patients completing FIT	Year 3 Repeat	# patients completing FIT
Repeat	screening Year 2	Completion	screening Year 3
Completion	# patients completing FIT Year 1	Rate =	# patients completing FIT Year 2
Rate =	with normal result		with normal result

We will compare initial FIT completion rates for the financial incentive plus organized outreach vs. organized outreach alone groups using a Chi-square test, with a 2-sided p value <0.05 considered statistically significant. The same approach will be taken for comparing repeat FIT completion rates for Years 2 and 3.

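### The Year 2 and Year 3 repeat-rate denominators have no age or invitation condition, so patients who turn 65 between rounds may count as non-repeaters

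*Combined protocol and SAP*

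**What the plan says.** - **Exit from the program** (Criteria for Exclusion of Subjects): "Once included, patients will remain in the program unless they no longer meet age criteria". The same section keeps outreach going for patients who leave the JPS assistance program or stop seeing primary care. Age is the only lost criterion that it says ends participation.
- **Age limit** (Criteria for Inclusion of Subjects): ages 50 to 64. "Patients older than 64 will be excluded because most of these patients would have screening access through Medicare insurance".
- **Repeat invitations** (Centralized processes to promote guideline-based follow up): a normal Year 1 test leads to "repeat screening invitations in Year 2 and Year 3". No age condition is restated there.
- **Repeat rates** (Evaluation Aim B): the Year 2 denominator is "patients completing FIT Year 1" with a normal result, and the Year 3 denominator is "patients completing FIT Year 2" with a normal result. Aim C uses the same definitions. The arms are compared by chi-square test.
- **Other rates, for contrast**: the initial rate in Aim B divides by the number "of patients sent FIT invitation Year 1". The Aim A denominator is limited to ages 50 to 64.
- **Censoring** (Screening Completion Follow Up): "For patients who die on follow up or who do not have additional health system encounters, follow up will be censored", at death or the last encounter respectively. Turning 65 is not listed.
- **Purpose** (Background Summary): "We must determine if participation rates remain high when screening is offered annually".

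**The concern.** A patient aged 64 at a normal FIT turns 65 within the year. On the natural reading of the inclusion and exclusion sections that patient gets no repeat invitation, yet the repeat-rate formula still has a place for them in the denominator. Unless they complete a FIT by another route within JPS, they count as having failed to take up an offer that was not made.

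The repeat rates are the only completion rates in Aims A and B with neither an age condition nor an invitation condition, and the plan gives no reason for the difference. Whether annual participation stays high is a stated program question. It will be answered from the absolute repeat rate, which the Background sets beside outside figures of 75% and 44%. The Background also says new interventions would be needed if repeat participation is poor. A rate that mixes refusal with loss of eligibility is less useful for that judgement.

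**Working it through.** **Plan's own figure.** There is none to reproduce. The Aim B sample-size section states that no formal power calculation is given for repeat completion.

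**Inputs from the documents.** Eligible ages 50 to 64, which is 15 single years of age; repeat participation 40% to 75% (Aim A); initial completion 33% (Aim A); abnormal FIT 12%, so 88% normal (FIT kit description); arms of 2,000 and 18,000 (Aim B).

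**Assumptions, not in the documents.** *f* is the share of prior-year normal completers who turn 65 before the next round. *g* is FIT completion among those who aged out. *r* is the repeat rate among those still eligible.

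**Formula.** Rate as written = *r*(1 − *f*) + *g f*. Shortfall = *f*(*r* − *g*).

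**Absolute rate:**

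| *f* | *g* | *r* = 40% reads | *r* = 75% reads | Shortfall (points) |
|---|---|---|---|---|
| 1/15 (6.7%) | 0 | 37.3% | 70.0% | 2.7 to 5.0 |
| 1/20 (5%) | 0 | 38.0% | 71.25% | 2.0 to 3.8 |
| 1/11 (9.1%) | 0 | 36.4% | 68.2% | 3.6 to 6.8 |
| 1/15 (6.7%) | 20% | 38.7% | 71.3% | 1.3 to 3.7 |

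For example, 0.40 × 14/15 = 0.373 and 0.75 × 14/15 = 0.700. In the last row, (0.40 − 0.20)/15 = 0.013 and (0.75 − 0.20)/15 = 0.037.

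**Numbers of patients.** Expected Year 2 denominators, taking 33% initial completion in both arms, are 2,000 × 0.33 × 0.88 = 581 (incentive) and 18,000 × 0.33 × 0.88 = 5,227 (outreach alone). At *f* = 1/15, about 39 and 348 of these would have aged out.

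**Arm comparison.** With the same *f* and *g* in both arms, the *g f* term cancels and a true difference *d* reads *d*(1 − *f*). So 10 points reads 9.3 and 5 points reads 4.7. Power with these denominators, *f* = 1/15 and *g* = 0:

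| Repeat rates compared | As written | Age-restricted denominator |
|---|---|---|
| 40% vs 45% | 59% | 61% |
| 70% vs 75% | 62% | 69% |
| 10-point difference | about 99% | about 99% |

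**No accumulation.** A patient who turns 65 before Year 2 will mostly not enter the Year 3 denominator. Each rate therefore carries about one year of ageing out.

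**The case against.** **The key steps are inferred.** No sentence says that aged-out patients get no repeat invitation, or that they stay in the denominators. The follow-up section promises repeat invitations without an age condition. Leaving the program could also be read as leaving its denominators: where the plan wants uninvited patients followed (initial non-responders), it says so. This stands in part. The formulas are nonetheless explicit and carry no such exclusion, and the follow-up section measures screening for everyone included. Taken literally they count these patients, so the plan must say which is meant.

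**Censoring may remove some of them.** Patients who move to Medicare may have no further JPS encounters. That is a partial answer only. A chi-square test on simple proportions has no stated way to use censored follow-up.

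**The denominator is a legitimate quantity.** Both outside repeat rates in the Background are described as shares of initial completers, with no continuing-eligibility condition mentioned. That is fair: repeat testing among all prior completers can be reported. It does not isolate the response to a repeat offer, which is the question the program asks.

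**A reader might infer more than the text supports.** It is tempting to say that repeat completion is definitely understated, by a predictable amount, and that the incentive comparison is biased. The documents support none of these. Non-invitation is implied and not stated. The age distribution of completers is not given, and a younger population would shrink the effect. Usual-care screening at JPS stays open to everyone, so *g* need not be zero. Ageing out should be similar across randomised arms. The plan also sets no threshold for an adequate repeat rate, so a shift of a few points would not overturn a stated decision rule.

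**Conclusion.** The point holds as a minor defect in the definition of the repeat rates. Read literally, the formulas count patients who have aged out, and who by implication were not re-invited, as non-repeaters. This lowers the absolute Year 2 and Year 3 repeat rates.

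The central estimate is 2.7 to 5.0 points across the plan's own 40% to 75% range. It assumes an even age spread over 50 to 64 and no FIT after ageing out. The scenarios examined span 1.3 to 6.8 points. If the sponsor does intend to re-invite patients after 65, the shortfall from lack of invitation disappears, but the exit rule and the follow-up section would then conflict.

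The effect on the incentive comparison, and on the 5-dollar versus 10-dollar comparison, is slight attenuation only. Initial completion and Aim A are not affected.

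**What to change.** 1. Reconcile the exit rule under Criteria for Exclusion of Subjects with the repeat-invitation text, so that it is clear whether a patient who turns 65 is due a repeat invitation.
2. Define each repeat-rate denominator as prior-year completers with a normal FIT who were still age-eligible when the repeat invitation was due.
3. Apply the existing rule for deaths in Screening Completion Follow Up, and say how it enters a simple proportion.
4. Report the number aged out, by arm and year.

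This changes the wording of two formulas. Date of birth is already on the list of variables to be abstracted, so no new data are needed. Date of birth is fixed before randomisation, so the age condition should not disturb the comparison of arms. The cost is a slightly smaller denominator: at 1/15, about 39 of 581 and 348 of 5,227 patients in Year 2. In the scenarios calculated, power is no lower than with the formula as written.

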	# patients eligible for
-	screening

We will compare groups using a Chi-square test, and use a 2sided p-value <0.05 to indicate a statistically significant difference between baseline and follow up screening rates. We predict the screening rate will increase by 10% from 39% at baseline to 49% at end of Year 3. The prediction is

based on several assumptions. First, we expect that initial FIT completion rates will be similar to the 33% rate observed in our prior CPRIT program among patients invited to FIT screening (Section A.2). Second, we expect colonoscopy follow up rates for patients with abnormal FIT will be 75%, similar to our prior program. Third, we considered various levels of repeat FIT participation rates. As is explained in Section A.3, there are limited data on "real world" repeat stool occult blood/FIT participation rates, with available estimates of repeat participation ranging from 40 to 75%^{33, 34}. We estimate this range of FIT repeat participation is consistent with a screening rate increase of 5 to 15%, from 39% at baseline, to between 43 and 54% at end of year 3. Thus, we conservatively predict an increase of 10%. As is noted below, we will have statistical power to detect the entire range of estimated screening rate increases.

Sample size for Evaluation Aim A. Unlike sample size estimates for clinical research trials, sample size estimates for these comparisons are not based on the minimum number of patients required to detect clinically significant differences in outcome rates. Rather, the sample size for these comparisons will be based on the number of patients potentially qualifying for screening outreach program. This is because the primary goal of CPRIT Evidence Based Prevention Programs is to maximize screening delivery. Nonetheless, because the sample we expect to identify is very large, we will have more than enough power to detect clinically significant differences in the outcome of interest. We estimate that at baseline and at follow up, at least 20,000 patients will qualify for our screening outreach program if not screening up-to-date (Table 1). With an expected sample of at least 20,000 patients eligible for screening at baseline and at end of year 3, assuming alpha=0.05, we will have over 90% power to detect our predicted screening rate increase of $\geq 10\%$, from 39% at baseline to 49% at end of Year 3 with a two-sided significance level. Moreover, with the expected sample sizes,

we will even have 90% power to detect a smaller screening rate increase of \geq 5% (Power was computed with nQuery Advisor Software v.7.0).

Evaluation Aim B) Compare rates of initial and repeat screening completion among 1) Patients offered a modest financial incentive to complete screening, in addition to outreach invitations (n=2,000), vs. 2) Patients offered outreach invitations alone (n=~18,000). The rate of initial screening completion will be defined by:

Initial	# patients completing a FIT
Screening	Year 1
Completion Rate =	# of patients sent FIT invitation Year 1

We will compare the initial screening completion rate for patients offered the financial incentive, in addition to screening outreach, to the initial rate for patients offered screening outreach alone using a Chi-square test of proportions, with a 2-sided p value <0.05

considered statistically significant. The rate of repeat screening for Years 2 and 3 will be defined by:

Year 2	# patients completing FIT	Year 3 Repeat	# patients completing FIT
Repeat	screening Year 2	Completion	screening Year 3
Completion	# patients completing FIT Year 1	Rate =	# patients completing FIT Year 2
Rate =	with normal result		with normal result

We will compare initial FIT completion rates for the financial incentive plus organized outreach vs. organized outreach alone groups using a Chi-square test, with a 2-sided p value <0.05 considered statistically significant. The same approach will be taken for comparing repeat FIT completion rates for Years 2 and 3.

Sample size for Evaluation Aim B. The sample size for this aim will be 2,000 for the financial incentive group plus outreach group, and at least 18,000 for the outreach group alone. The sample size for the financial incentive group was chosen based on sample size required for sufficient power to detect expected differences between offers of \$5 and \$10 gift card incentives outlined in Aim C below. The sample size for the outreach group alone was based on including all patients included in the screening outreach program who will not receive financial incentives. With 2,000 patients assigned to the financial incentive plus outreach group, and 18,000 patients assigned to the outreach alone group, we estimate over 90% power to detect differences in initial screening participation of 5% or more at a 5% two-sided significance level. Thus, we will have more than enough power to detect clinically meaningful differences of 10% or more in initial FIT completion. Because of the lack of prior data on repeat FIT participation rates, and under the sample size discussion for Evaluation Aim A above, we do not present formal power calculations for comparisons of repeat FIT completion rates, but expect that we will be able to make meaningful comparisons based on the large number of patients included for evaluation.

Evaluation Aim C) Compare rates of initial and repeat screening among patients receiving \$5 vs. \$10 financial incentives in addition to outreach invitations. For this comparison, we will use the same definitions outlined under "Evaluation Aim B" above for the initial screening completion rate, and the Year 2 and 3 repeat completion rates. For these outcomes, we will compare the outcome rate for patients receiving the \$5 vs. \$10 incentive, using a Chi-square test of proportions, with a 2-sided p value <0.05 considered statistically significant.

Sample size for Evaluation Aim C. The sample size for Evaluation Aim C is based on comparing the initial screening participation rate between the \$5 vs. the \$10 incentive groups. As is outlined in Section A.3, previous data suggest that financial incentives are effective for promoting complex healthy behaviors such as quitting smoking³⁹⁻⁴¹. Further, we believe that incremental (modest) incentives are likely to significantly increase screening completion. First, we assumed that a 10% or more difference in initial screening participation would be clinically meaningful. Second, we assumed that the screening completion rate associated with the \$5 group would be 43%, and that the rate for the \$10 group would be at least 53%. The 43% rate was chosen because our response to FIT invitations with our prior outreach program was 33%, and we would consider a 10% or more increase Version 8, June 29, 2015

in screening completion associated with the \$5 intervention over organized outreach alone to be clinically meaningful. Similarly, the 53% rate was chosen for the \$10 group because we would consider a 10% or more increase in screening completion associated with the \$10, rather than the \$5 group to be clinically meaningful. Under these assumptions, with an alpha=0.05, we estimated 1090 patients (n=545 in the \$5 group and n=545 in the \$10 group) would be required for 90% power to detect a statistically significant difference of 10% or more in initial screening participation. Because we recognize uncertainty in the estimating the expected difference between the two groups, and because we wanted to increase our ability to conduct exploratory comparisons of repeat FIT participation rates associated with the \$5 and \$10 groups, we increased the planned sample receiving financial incentives to 2,000 (n=1,000 in the \$5 group and n=1,000 in the \$10 group). Thus, we will have more than enough power to detect differences of 10% or more in initial screening participation.

Evaluation Aim D) Assess all CPRIT required outcomes, including increase in early stage cancer detection from baseline, as well as systems changes required to boost screening. To assess increase in early stage cancer detection from baseline, we will compute proportion of CRC patients with early stage cancer at baseline and at end of Year 3. JPS Cancer Registry data will be used for this computation. Rate of early stage cancer will be defined as:

Early Stage	# CRC patients with SEER Summary
Cancer	Stage 0 or Stage 1
Detection Rate =	# CRC patients

program at JPS to other safety-net systems.

We will use a Chi-square test of proportions for comparing groups, and a p value <0.05 to signify statistical significance.

To assess systems changes required to boost screening, we will plan additional evaluations focused on the JPS health system. In addition to evaluating outcome change (as described above), it is also important to evaluate changes in processes related to transferring and expanding our outreach program at JPS. The purpose of this process evaluation is to gather information about the roll out process to enhance sustainability of the screening program, and enable translation of this program to other safety-net settings. To meet these objectives, we will monitor the screening program on a real-time basis. During weekly meetings between UTSW nurse (TBA) and JPS screening outreach team, the UTSW nurse will ask members of the outreach team about their experience with the program. She will maintain a detailed log of problems and successes. She will also document strategies and workarounds that JPS staff develop to tailor the program to their needs and resources. Similarly, barriers and facilitators of the outreach program at the health system level identified during JPS physician champion meetings with the principal investigator will be documented. Sustainability of the program will be enhanced because JPS staff will have access to systematically collected information about on the ground strategies that worked and did not work at the screening delivery level as well as at the health system level. In

addition, this information will also enable us to apply our knowledge of successfully establishing this

Secondary analyses. We plan to conduct several secondary analyses. First, we recognize that results from Evaluation Aim A, in which baseline screening rates will be compared to follow up screening rates at year 3, could be confounded by time trends in CRC screening rates, which generally have been increasing over time. Accordingly, we will compare the observed rate of CRC screening in Year 3 to the expected rate of CRC screening based on time trends in screening at JPS. The expected rate will be estimated using the secular trend for CRC screening using annual screening rates for each of the 7 years 2006-2011 prior to start of our prevention program in 2012. All rates will be standardized by gender and age strata (50-54, 55-59, and 60-64 years) to the population distribution of men/women and these age strata for 2012, and a standardized incidence ratio (SIR) will be computed. An SIR greater than 1, with an associated 95% confidence interval that does not cross 1 will be interpreted as evidence to support impact of our outreach intervention beyond time trends in CRC screening rates. We have previously used this approach to assess impact of a University of Texas health plan policy that waived copays for colonoscopy screening on CRC screening rates which began in 2009, in which we compared colonoscopy uptake 2002-2008 to uptake after policy institution⁴⁶.

Version 8, June 29, 2015

Second, to identify factors independently associated with screening outcomes, we will construct several logistic regression models. For example, to identify predictors of initial screening completion, we will create a model using initial screening completion rate as the primary outcome (dependent) variable, and several potential predictors of completion. Predictors considered for model inclusion will include age, sex, race/ethnicity, frequency of primary care visits, exposure to the screening outreach program, and exposure to financial incentives. A similar model will be created with the outcome of programmatic screening as the dependent variable. For these exploratory analyses, 2-sided p values of 0.05 will be considered statistically significant.

Third, we will quantify the number of patients who have CRC and potentially precancerous polyps detected through screening outreach. CRC and polyp data will be collected by reviewing all colonoscopy and associated pathology reports for patients who undergo colonoscopies after having abnormal FIT tests. Additionally, we will query the JPS tumor registry to identify any program participants who had CRC diagnosed, and determine, through chart review, whether the CRCs were detected as a result of our screening outreach or through other mechanisms. With our plan to invite over 20,000 patients, taking into account our prior rates of FIT screening participation (33%), abnormal FIT results (12%), and detection rates of CRC (4.8%) and adenomas (46%) after abnormal FIT, we estimate that 38 patients with CRC and 364 patients with adenomas will be identified through our program.

REFERENCES

- 3. (2012). StatBite: National Costs for Cancer Care in 2010 in Billions of Dollars by Cancer Site. J Natl Cancer Inst 104, 13.
